9. STUDY POPULATION

9.1 Subject Disposition

The number of subjects screened, the number of screen failures, the number of subjects who entered the MTX Run-in period and the number of subjects who discontinued the MTX Run-in period will be summarized. The number of subjects in each analysis set, the number of subjects who entered the Pegloticase + MTX treatment period, the number of subjects who completed and discontinued from the Pegloticase + MTX treatment period (separately for Weeks 1-24 and the optional period Weeks 24-48), and the number of subjects who completed and discontinued the study, along with the reasons for discontinuation for Week 24 and Week 48 respectively will be summarized.

Subject study duration in weeks will be summarized for subjects in the ITT analysis set. The number of subjects with results for each scheduled visit will also be presented. A subject will be considered to have completed a visit if they had any results recorded in the eCRF for the visit. Subject study duration will be calculated from the first visit in the MTX Run-in Period (Week -6) to the end of trial visit date, on which the end of study assessment (i.e., Week 48) is performed.

9.2 Protocol Deviations

Major protocol deviations that could potentially affect the efficacy or safety conclusions of the study will be identified before database lock. Major protocol deviations are detailed in the Protocol Deviation Management Plan and may include, but are not limited to:

- Subjects who did not satisfy selected key inclusion and exclusion criteria;
- Subjects who developed withdrawal criteria during the study but were not withdrawn;
- Subjects who received an incorrect dose;
- Subjects who received an excluded concomitant treatment.

The number of subjects experiencing any minor protocol deviation, any major protocol deviation and any deviation related to COVID-19, along with the number of protocol deviations, will be

presented for subjects in the ITT analysis set. Major protocol deviations will be further summarized by deviation category.

All protocol deviations, including the deviation designation (major or minor), category, subcategory, and indication of whether the deviation was related to COVID-19 will be presented in a data listing.

9.3 Eligibility

A listing of subjects not fulfilling all eligibility criteria will be created.

9.4 Demographic and Baseline Characteristics

Demographic and baseline data and gout history will be summarized using descriptive statistics.

Demographic variables include age (in years), sex, ethnicity and race.

Other baseline characteristics include height (in cm), weight (in kg), body mass index (BMI in kg/m²), childbearing potential (for females only), and substance use history.

Descriptive statistics will be presented for age, height, weight, BMI, sex, ethnicity, race, childbearing potential (for females only), tobacco use, alcohol use, and other substance use. Demographic and baseline characteristics will be summarized for the ITT analysis set.

Gout history variables will include time since first gout attack (in years), time since first gout diagnosis (in years), presence of uric acid crystals confirming diagnosis, number of acute flares in past 12 month, number of acute flares in past 6 months, pattern of flares, typical severity of acute flares, chronic gout synovitis/arthropathy, prior or current tophi, history of overnight hospital stay for gout, history of surgery for gout (excluding arthrocentesis), history of kidney stones, kidney function impacted by gout, number of episodes of renal colic in the past year, and urate lowering therapy history (allopurinol, febuxostat, and other urate lowering therapy for gout).

Time since first gout attack will be calculated as: (informed consent date - date of first gout attack + 1) / 365.25, rounded to two decimal places. In the event of a partial first gout attack date, the earliest possible date implied by the data provided will be imputed.

Time since first gout diagnosis will be calculated as: (informed consent date - date of first diagnosis + 1) / 365.25, rounded to two decimal places. In the event of a partial diagnosis date, the earliest possible date implied by the data provided will be imputed.

Gout history will be summarized for the ITT analysis set.

Medical/Surgical history

The verbatim term of the medical/surgical history condition/event will be coded using Medical Dictionary for Regulatory Activities (MedDRA) 23.1.

Medical/surgical history will be summarized in the ITT analysis set and will be ordered alphabetically by system organ class (SOC) and by preferred term (PT) within system organ class.

Medical/surgical history terms and tobacco and alcohol history will be listed.

Pegloticase History

Pegloticase use history will be summarized in the ITT analysis set using descriptive statistics. Pegloticase history variables will include: time since last dose to screening, duration of treatment, dosing frequency, total number of infusions, reason for stopping pegloticase treatment, sUA stopping rule met (if applicable), and infusion reaction severity (if applicable).

9.5 Prior and Concomitant Medications

Prior and concomitant medication verbatim terms in the eCRFs will be mapped to Anatomical Therapeutic Chemical (ATC) level 4 and preferred names using the WHODRUG Global B3 Sep2020.

Partial dates will be imputed. For details on imputation rules, refer to [Appendix A: Presentation of Data and Programming Specifications](#). Imputed dates are only used for classification of medication into prior or concomitant medication; no other calculation such as durations will be done.

Prior medications are defined as any medication with a start date prior to the date of first dose of treatment in the MTX Run-in Period.

Concomitant medications during the MTX Run-in Period are defined as:

- Medications with a start prior to the first dose of MTX in the MTX Run-in Period that are ongoing or with a stop date after the first dose of MTX in the MTX Run-in Period.
- Medications with a start date after the first dose of MTX in the MTX Run-in Period but before the first dose of pegloticase and before 30 days after the last MTX dose, for subjects who did not receive an infusion of pegloticase.

Concomitant medications during the Pegloticase + MTX Period are defined as:

- Medications with a start prior to the first dose of pegloticase that are ongoing or with a stop date after the first dose of pegloticase.
- Medications with a start date after the first dose of pegloticase but before 30 days after the last dose of pegloticase.

Medications with a partial start date where month and year of start match the month and year of first MTX date and match the month and year of first Pegloticase infusion will be classified as being concomitant in both the MTX Run-in Period and in the Pegloticase + MTX Period. In general, medications can be classified in one or more of prior, concomitant during the MTX Run-in Period, and concomitant during the Pegloticase + MTX Period categories.

Summaries will be presented separately for prior medications, concomitant medications during the MTX Run-in Period, and concomitant medications during the Pegloticase + MTX Period. Summaries will be presented by ATC Level 4 term and preferred drug name. Medication summaries will be sorted alphabetically by ATC Level 4 and by preferred drug name within ATC Level 4. Subjects will be counted only once for each medication class and each preferred drug name.

Concomitant procedures and prior and concomitant medications will be presented in a listing.

10. EFFICACY ANALYSES

The ITT analysis set will be used to assess efficacy endpoints. The estimand for the primary analysis will use the Treatment Policy Strategy (data will be used regardless of whether an intercurrent event occurred) for most intercurrent events; the intercurrent event of treatment or study discontinuation related to COVID-19 (leading to data that are missing completely at random) will be addressed with a While-on Treatment Strategy (only values prior to occurrence of intercurrent event will be used).

10.1 Efficacy Variables

10.1.1 Primary Efficacy Endpoint

The primary efficacy endpoint is the Month 6 responder rate, defined as the proportion of subjects achieving and maintaining sUA < 6 mg/dL for at least 80% of the time during Month 6. The Month 6 responder rate will consider pre and post infusion results at Week 20, results at Week 21, pre and post infusion results at Week 22, results at Week 23, and pre-infusion results at Week 24. The amount of time that sUA is < 6 mg/dL (using linear interpolation if necessary) will be calculated and divided by the total amount of time from the first to the last observed sUA value in corresponding time range (missed values in this time range will be ignored for purposes of this calculation). If the amount of time that sUA is < 6 mg/dL is $\geq 80\%$, then the subject will be considered a responder.

10.1.2 Secondary Efficacy Endpoints

- Month 3 responder rate – defined as the proportion of subjects achieving and maintaining sUA < 6 mg/dL for at least 80% of the time during Month 3. The Month 3 responder rate will consider pre and post infusion results at Week 10, Week 12, and Week 14 and also

the between-visit non-infusion results at ~24 hours and ~168 hours after doses at Week 10 and 12.

- The proportion of subjects who experienced any of the following events from Day 1 to Week 24: IR leading to discontinuation of treatment, anaphylaxis or meeting Individual Subject sUA Discontinuation Criteria (defined as the lowest available interim sUA value after the pegloticase infusion at Week 2, 4, 6, 8, 10 or 12 is less than a 50% reduction from the highest sUA value measured between Screening and pre-infusion on Day 1).
- The change from Baseline in urate deposition volume, measured by dual-energy computed tomography (DECT) scan. The DECT will include, at a minimum, hands, feet and knees and other anatomical areas as clinically indicated.
- Change from baseline to each postbaseline assessment in HAQ-DI score. The HAQ-DI assesses the subject's level of functional ability and includes questions of fine movements of the upper extremity, locomotor activities of the lower extremity and activities that involve both upper and lower extremities. There are 20 questions in 8 categories of functioning including dressing, rising, eating, walking, hygiene, reach, grip and usual activities [Cole, 2006]. The subject's ability to accomplish each activity in the past week is indicated as: without any difficulty, with some difficulty, with much difficulty and unable to do. Any devices that are usually used to complete activities and any categories for which help from another person is needed is also assessed. See details on scoring of HAQ-DI in [Appendix A](#).
- Change from baseline to each postbaseline assessment in HAQ Pain Score. The HAQ Pain question asks, "How much pain have you had in the past week?" on a scale of 0-100 where 0 represents no pain and 100 represents severe pain.
- Change from baseline to each postbaseline assessment in HAQ Health score. The HAQ Health question asks, "Please rate how well you are doing on a scale of 0 to 100 (0 represents 'very well' and 100 represents 'very poor' health)".

10.1.3 Exploratory Efficacy Endpoints

The text 'CCI' is displayed in a large, bold, red font. It is positioned on a solid black rectangular background. The letters are slightly rounded and have a thick stroke.

10.2 Baseline Values

Unless otherwise noted, baseline is defined as the last non missing value recorded before the first infusion of pegloticase.

10.3 Adjustments for Covariates

Analyses of the efficacy endpoints will not include adjustments for covariates.

10.4 Handling of Dropouts or Missing Data

No imputations will be made for missing values. In general, summaries will be based on observed data only. See further details on missing data for the primary endpoint in [Section 11.2](#).

10.5 Interim Analysis and Data Monitoring

No formal interim analysis is planned for this study.

Safety data will be summarized for safety assessments conducted after 7 and 10 subjects in Cohort 1 complete 6 infusions and after 3, 6, 10, 15 and 20 subjects in Cohort 2 complete 6 infusions. The results of these analyses will determine if enrollment will continue in each cohort. Efficacy and safety data may be summarized periodically throughout the trial to support scientific publications. Additionally, safety data will be summarized regularly for safety monitoring. Final analysis will occur when all subjects have completed the trial. No Type 1 error rate adjustments will be made due to multiple summaries.

10.6 Examination of Subgroups

No subgroup analysis is planned for this study.

10.7 Multiple Comparison/Multiplicity

No Type 1 error rate adjustments will be made due to multiple comparisons.

10.8 Multicenter Studies

Data from all sites will be summarized together for analyses.

11. METHODS OF EFFICACY ANALYSIS

11.1 Handling Rules for sUA Values

Serum samples for measurement of sUA levels will be collected at the Screening, Week -6 (prior to the first dose of MTX) and Week -2 Visits. On Day 1, a pre- and post-infusion sUA will be collected to be shipped to the central laboratory. For the remainder of trial visits beginning at Week 2 during the Pegloticase + MTX Treatment Period, 2 sUA samples will be collected within 48 hours prior to each pegloticase infusion. One sample will be for sUA testing at the site's local laboratory and the second sample will be sent to the central laboratory (the central laboratory sample may be drawn separately from the local collection). Additional serum samples for sUA levels will be collected after the end of each pegloticase infusion prior to discharge at Weeks 10, 12, 14, 20, 22, 32, 34, 44 and 46. Single serum samples for measurement of sUA will also be collected at non-infusion visits at Weeks 21 and 23 and at the End of Pegloticase (if applicable) or the Week 24 or 48/End of Trial/ET Visit. Serum for sUA analysis will also be collected at Day 1 (~24 hours) post-infusion, Day 4 (~96 hours) post-infusion, Day 7 (~168 hours) post-infusion, and Day 10 (~ 240 hours) post-infusion following the first 4 pegloticase infusions at Day 1, Weeks 2, 4, 6, . , Serum for sUA analysis will also be collected at Day 1 (~24 hours) post-infusion, and Day 7 (~168 hours) post-infusion following the Week 8, 10 and 12 infusions. If infusion intervals of less than 2 weeks should occur due to scheduling issues, the 1st day (~24hours) samples must be obtained at a minimum and also the 7th day (~168 hours) if feasible.

Prior to Week 22, subjects whose lowest available interim sUA value (typically the 1st day [~24 hours] after infusion) after the pegloticase infusion at Week 2, 4, 6, 8, 10 or 12 is less than a 50%

reduction from the highest sUA value measured between Screening and pre-infusion on Day 1 will discontinue treatment and complete the End of Pegloticase Visit within 2 weeks of the last infusion, but remain in the trial for biweekly visits, including the Week 24/End of Trial/Early Termination and 30-Day Post-Treatment Follow-up Visits.

Samples that result in discordant results between local and central laboratories will be evaluated and discussed with the Investigator and the Sponsor's Medical Monitor on a case-by-case basis to determine whether the subject should continue on trial or proceed to the End of Pegloticase Visit.

For the determination of sUA responder endpoints, scheduled assessments of sUA and unscheduled assessments of sUA, reported by the central laboratory, will be used. Local laboratory-processed pre-infusion sUA results will be used only when the central laboratory-processed value at a time point is not available, but the local lab-processed pre-infusion value, collected at the same time point, is available.

When the central laboratory or local laboratory reports a value for sUA as being lower than the lab assay's limit of quantification (e.g. “<0.02”), zero will be used as the numeric value for the purpose of determining response and for summaries of observed values and the change from baseline. When the central laboratory or local laboratory reports a value for sUA as being higher than a certain value of quantification (e.g. “> 8.7”), the numeric value (e.g. 8.7) after ‘>’ is used for the purpose of determining response and for summaries of observed values and the change from baseline.

11.2 Primary Efficacy Endpoint and Analysis

The primary efficacy endpoint is the proportion of Month 6 (Weeks 20, 21, 22, 23 and 24) responders, defined as subjects achieving and maintaining sUA < 6 mg/dL for at least 80% of the time during Month 6.

The sUA concentrations vs. time (collected to the nearest minute in the CRF) curve will be used to estimate the proportion of time that the sUA is < 6 mg/dL using the available pre-infusion, non-infusion, and post-infusion samples with non-missing sUA values. Central laboratory results from visits at which an infusion was not performed (e.g., subject discontinued pegloticase but remained in study or unscheduled visits) will be used when available.

CCI

CCI

[REDACTED]

[REDACTED]

[REDACTED]

[REDACTED]

[REDACTED]

[REDACTED]

[REDACTED]

CCI

If the subject's proportion of hours, P, is greater than or equal to 80% the subject will be called a responder for the primary efficacy endpoint. A subject with the proportion of hours, P, less than 80% will be counted as a non-responder. Any subject who meets the individual subject sUA discontinuation criteria or discontinues pegloticase with reason of 'Lack of Efficacy', prior to Week 24 will be counted as a non-responder.

For subjects who postponed or missed visits due to COVID-19, only visits occurring prior to any disruption of treatment (> 21 days between infusions) or cessation in treatment will be used for the primary analysis. Any results following the disruption in treatment will be set to missing. Subjects with disrupted treatment due to COVID-19 at any point prior to the Month 6 period will not be included in the primary analysis.

The proportion of hours during the period during which the sUA was less than 6 mg/dL will be summarized using descriptive statistics. If a subject has ≤ 1 data point in the period, then the proportion of hours will not be calculated. The number and proportion of subjects that discontinued treatment due to the stopping rule will be summarized. The number and proportion of responders will be summarized along with a 95% exact (Clopper-Pearson) confidence interval (CI) for the proportion. In addition, the number and proportion of subjects missing all data in the analysis period, subjects with only one measurement above the cutoff in the analysis period, and subjects with only one measurement below the cutoff in the analysis period will be summarized.

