22/85 (26%) of subjects receiving the 8 mg every 2 weeks regimen. There was no specified definition of anaphylaxis in the Phase 3 protocols and no investigator-reported events of anaphylaxis in the Phase 3 trials with pegloticase. However, in a post hoc review applying the National Institute of Allergy and Infectious Disease and the Food Allergy and Anaphylaxis Network criteria (Sampson et al, 2006), it was determined that across the Phase 2 and Phase 3 program, anaphylaxis occurred in 6.5% of subjects treated with pegloticase every 2 weeks. Anaphylaxis generally occurred within 2 hours after treatment. Manifestations included wheezing, peri-oral or lingual edema or hemodynamic instability, with or without rash or urticaria. All of these events had relatively rapid resolution with cessation of infusion.

In a post hoc analysis, the apparent role of immunogenicity in both loss of urate-lowering effect and incidence of IRs was appreciated. Only 2% of subjects with anti-pegloticase antibody titers exceeding 1:2430 maintained a urate-lowering response to pegloticase compared with 63% of subjects who were treated for at least 2 months without developing high-titer antibodies ($p<0.001$) (Sundy et al, 2011). The incidence of IRs was higher among subjects who developed high-titer antibodies compared with those who had titers that did not exceed 1:2430 (60% vs 19%; $p <0.001$) (Sundy et al, 2011). In addition, most IRs occurred when sUA levels were >6 mg/dL. Retrospective analyses showed that the loss of urate-lowering efficacy, as reflected by sUA of >6 mg/dL, preceded a subject's first IR, whenever it occurred, in 20 (91%) of 22 subjects treated with pegloticase every 2 weeks.

Reducing anti-drug antibodies with concomitant administration of the immunomodulatory agent methotrexate (MTX) has been shown to be useful with other infused products that lead to immunogenicity, such as adalimumab, in the setting of rheumatoid arthritis treatment (Burmester et al, 2015).

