During the Pegloticase + MTX Treatment Period, subjects will be instructed to inject MTX weekly on the same day each week, within 1 to 3 days prior to each pegloticase infusion (on the weeks when pegloticase is administered); however, if a subject does not do so, MTX must be injected ≥ 60 minutes prior to each pegloticase infusion. One additional weekly dose of MTX will be injected after the last pegloticase infusion for subjects who have not stopped pegloticase due to individual subject sUA discontinuation criteria. If the subject discontinues pegloticase due to the stopping rule or other reason, MTX and folic acid should also be discontinued.

After Day 1, if a subject becomes unable to tolerate MTX, the folic acid dose can be increased, an alternative folate supplement may be used and/or the MTX dosage may be reduced or discontinued based on pre-defined criteria (see [Section 9.4.6.3.2.2](#) for detailed instructions) and the subject may remain in the trial and continue pegloticase infusions. Every attempt should be made to re-start the MTX in subjects once their MTX-associated symptoms have improved or their laboratory tests have normalized.

The Investigator will review the subject clinical status and [CCI](#) ([Appendix 17.8](#)) at Week -6; prior to pegloticase infusion at the Week 24 and Week 36 Visits (subjects who may gain further benefit beyond 12 infusions and elect to receive pegloticase + MTX during the Optional Pegloticase + MTX Extension Period); and at the End of Pegloticase (if applicable) and Week 24 or 48/End of Trial/Early Termination Visits.

After the Week 24 or 48 Visit (or End of Pegloticase Visit [if applicable]) or upon pegloticase discontinuation, subjects should resume regular care for gout per the judgment of the treating physician, including resumption of urate-lowering therapy, if appropriate.

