9.3.3.1 Removal of Subjects From Pegloticase Therapy

For subjects who do not complete therapy through Week 24 or 48, the reason for discontinuation from pegloticase therapy should be recorded on the eCRF using 1 of the following categories:

- Lost to Follow-up. The subject does not return to the clinic for scheduled assessments and does not respond to the site's attempts to contact the subject.
- Lack of Efficacy.
- AE. The subject experiences an AE that imposes an unacceptable risk to the subject's health (e.g., anaphylactic reaction), or the subject is unwilling to continue therapy because of an AE. Subjects who discontinue due to an AE should be followed until resolution or stabilization of the AE, or an adequate explanation for the event is obtained.
- Physician Decision. The Investigator has determined that pegloticase administration poses an unacceptable risk to the subject (specify reason).
- Withdrawal by Subject. Subject refusal of additional therapy (specify reason).
- Trial Terminated by Sponsor. The Sponsor, IRB or regulatory agency terminates the trial.
- Pregnancy.
- Death.

9.3.3.1.1 Trial Considerations for Subjects Ending Pegloticase Infusions Prior to Week 24 or Week 48

- MTX, along with folic acid, will be discontinued at the time of cessation of pegloticase infusions prior to Week 24 or 48.
- All subjects will complete the End of Pegloticase Visit and will remain in the trial through Week 24 (if End of Pegloticase Visit occurred before Week 24) regardless of whether they stop infusions due to sUA stopping rules or other reason (e.g., withdrawal of consent for pegloticase infusions).
- Subjects are encouraged to continue to participate in all visits, including the 30-Day Post-Treatment Follow-up and Week 24/End of Trial/Early Termination Visits, but are especially encouraged to complete trial visits at the trial site for key efficacy and safety assessments at Weeks 10, 12, 14, 20, 21, 22, 23 and 24, so that sUA laboratory and other key assessments can be completed. During visits between these key efficacy and safety collection visits, in subjects who have stopped infusions, subjects may complete trial visits in person or via telephone to collect AE, concomitant medication and gout flare information.
- Activities related to pre-/post-infusion monitoring or medication dispensation will not be completed once a subject has stopped pegloticase infusions. These activities include:
 - MTX compliance/reconciliation;
 - IR prophylaxis;

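### In the visible text of SAP 11.2, a subject who stops pegloticase early for a reason such as an adverse event and then starts another urate-lowering drug can still be counted as a pegloticase + MTX responder

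*SAP*

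**What the plan says.** SAP 10 adopts a treatment policy strategy for most intercurrent events, meaning that "data will be used regardless of whether an intercurrent event occurred". The one visible exception is COVID-19 discontinuation.

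SAP 10.1.1 builds the Month 6 endpoint from "pre and post infusion results at Week 20, results at Week 21, pre and post infusion results at Week 22", then Week 23 and the Week 24 pre-infusion sample. SAP 11.2 calls a subject a responder if sUA is below 6 mg/dL for at least 80% of the observed hours, and does not compute the proportion with one value or none. Central results from visits without an infusion ("e.g., subject discontinued pegloticase but remained in study or unscheduled visits) will be used when available") enter the calculation.

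Two visible rules override this. One makes a non-responder of "Any subject who meets the individual subject sUA discontinuation criteria or discontinues pegloticase with reason of 'Lack of Efficacy', prior to Week 24". The other concerns COVID-19: "Subjects with disrupted treatment due to COVID-19 at any point prior to the Month 6 period will not be included in the primary analysis".

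Protocol 9.3.3.1 says that the "reason for discontinuation from pegloticase therapy should be recorded on the eCRF using 1 of the following categories". Besides lack of efficacy, the list has adverse event, physician decision, withdrawal by subject and pregnancy, among others. Early stoppers stay in the trial to Week 24 and are especially encouraged to attend the Week 20 to 24 visits (9.3.3.1.1).

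On other urate-lowering therapy, Protocol 9.1 says that "upon pegloticase discontinuation, subjects should resume regular care for gout per the judgment of the treating physician, including resumption of urate-lowering therapy, if appropriate". Section 9.4.1.2 says the same. The prohibition in 9.4.10 ends with pegloticase and MTX. Section 9.3.3.1.1 names the Week 24 or 48 visit as the earliest point for restarting oral therapy, with the End of Pegloticase Visit as a bracketed alternative. Inclusion criterion 7 (9.3.1) points the other way: subjects agree to stay off such therapy throughout the Treatment Period.

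**The concern.** The primary objective (SAP 3.1) is a response rate above 20% in subjects receiving pegloticase with MTX. There is no control arm in which another drug's effect could cancel out. If an early stopper restarts a different urate-lowering drug and has normal sUA in Weeks 20 to 24, the visible rule credits that result to pegloticase + MTX. No visible text names the restart as an intercurrent event.

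The adverse-event route follows from the protocol itself: confirmed anaphylaxis ends pegloticase dosing (9.4.6.3.2.1). The secondary composite in SAP 10.1.2 groups anaphylaxis and infusion reactions leading to discontinuation with meeting the sUA criteria, but the primary rule makes only the last of these a non-response. The same subject could therefore meet the adverse composite and be a primary responder.

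At stake is whether a result at or just above the success threshold reflects the trial treatment.

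**Working it through.** **1. The plan's own figure.** SAP 5 and Protocol 9.6.9 state that 12/30 gives a lower bound of about 23%. The exact (Clopper-Pearson) lower bound for x of n is the 0.025 quantile of Beta(x, n − x + 1).
- 12/30: Beta(12, 19) gives 22.66%, which reproduces the stated figure.
- 11/30: Beta(11, 20) gives 19.93%, below 20%.

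The binomial tail at a true rate of 20% agrees: P(X ≥ 12) = 0.0095 and P(X ≥ 11) = 0.0256. Twelve is the smallest count that succeeds.

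**2. Conditions for a false responder.** All of these must hold:
- pegloticase permanently stopped before the Week 22 infusion visit;
- recorded reason other than 'Lack of Efficacy';
- sUA discontinuation criteria never met;
- not covered by the COVID-19 rule;
- other urate-lowering therapy started before the last Month 6 sample;
- at least 2 sUA values in the period, with sUA below 6 mg/dL for at least 80% of the time.

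**3. Size of one case.** Each adds 1/30 = 3.3 percentage points. If exactly one exists, it changes the conclusion only when the genuine count is 11. P(X = 11 | n = 30, p):

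| True rate p | 20% | 30% | 35% | 40% | 50% |
|---|---|---|---|---|---|
| P(X = 11) | 1.6% | 11.0% | 14.7% | 14.0% | 5.1% |

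These are conditional on one case existing. The documents give no such probability, so take q = 5%, 10% or 25% as assumptions. Then q × P(X = 11) over true rates of 30% to 40% is:
- q = 5%: 0.55% to 0.74%
- q = 10%: 1.1% to 1.5%
- q = 25%: 2.8% to 3.7%

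**4. Effect on false-positive risk.** Let the genuine rate be 20% and let k be the expected number of false responders among 30 (assumed range 0 to 1). The counted rate is 0.20 + k/30.

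| k | 0 | 0.25 | 0.5 | 0.75 | 1 |
|---|---|---|---|---|---|
| P(X ≥ 12) | 0.95% | 1.3% | 1.8% | 2.4% | 3.1% |

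The 2.5% level is reached at k ≈ 0.80, which is 0.80/30 = 2.7% of subjects.

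**5. Would the planned tables show it?** SAP 9.5 counts a medication as concomitant in the pegloticase period only if it starts within 30 days of the last pegloticase dose. Week 24 is Day 169 (SAP Table 8), so the uncovered gap is 169 − (last infusion day + 30):
- last infusion Week 10 (Day 71): 68 days
- Week 14 (Day 99): 40 days
- Week 18 (Day 127): 12 days

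A restart in that gap is listed but does not reach the summary table.

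**The case against.** **This is what treatment policy means.** Restarting another drug falls under the declared default and need not be named to be handled. That is correct as a description of the strategy, and replacing it for one event is an estimand choice. It does not settle the matter. The objective attributes response to subjects receiving pegloticase with MTX, and SAP 11.2 already departs from treatment policy through its own override.

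**The path is narrow.** This stands. Late loss of response can be recorded as lack of efficacy, which the override catches. Many subjects stopping for infusion reactions may already have met the sUA criteria: in earlier trials loss of urate lowering came before the "first IR, whenever it occurred, in 20 (91%) of 22 subjects treated with pegloticase every 2 weeks", although that used a 6 mg/dL cut-off and this trial uses a 50% reduction. Inclusion criterion 4 requires xanthine oxidase inhibitors to have failed or be contraindicated.

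**Permission to restart is unclear.** This also stands. Inclusion criterion 7 and the first clause of the restart rule in Protocol 9.3.3.1.1 point against a restart before Week 24; 9.1, 9.4.1.2 and 9.4.10 point towards it. Reconciling these passages could close the path without any change to the analysis.

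**Redaction.** Text is blacked out inside SAP 11.2, between the use of off-treatment samples and the responder rule, and again after the additional sUA analyses in 11.3. A relevant rule may be there.

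**Cases could be found by hand.** With 30 subjects, medication listings and by-subject sUA plots would allow it. That helps interpretation but does not change the primary classification.

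**Conclusion.** On the visible text the point holds in a limited form: the rule as written can credit another drug's effect to pegloticase + MTX. It can change the conclusion only near 12/30, and each case adds 3.3 percentage points. The frequency is not given and is probably low. The probabilities above rest on assumed values and independent binomial responses.

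Three stronger readings are tempting, and the documents do not support them:
- *The primary result is materially inflated, or the error rate is breached.* Over most of the assumed range (k below about 0.80) the false-positive risk stays under 2.5%, and nothing in the documents indicates that k is higher.
- *The plan has no rule for this.* The redactions prevent that conclusion.
- *The mismatch with the protocol adds to the inflation.* Protocol 9.6.5.1 lacks the existing non-responder override, yet SAP 15 reports no changes. The override can only lower the rate, so this is a separate documentation point and carries no weight in the severity.

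The finding is minor, between optional and should-fix.

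**What to change.** In SAP 11.2, extend the existing non-responder override to subjects who start other urate-lowering therapy after permanent pegloticase discontinuation and before their last Month 6 sUA sample. Define permanent discontinuation here as a last infusion before the Week 22 visit, whatever the number of skipped infusions. In addition:
- Leave the COVID-19 rule unchanged.
- Apply no truncation or other new rule to subjects treated through Week 22. Dropping their later samples could raise the rate, because rising sUA that prompted the new therapy would be removed.
- Report the treatment-policy rate as a sensitivity analysis.
- Summarise urate-lowering therapy use through Week 24.

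The sponsor must reconcile inclusion criterion 7 with the synopsis and Protocol 9.1, 9.3.3.1.1, 9.4.1.2 and 9.4.10. No position is taken here on when therapy may restart. As a separate housekeeping matter, list the override in SAP 15.

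The cost is SAP wording and some programming on concomitant-medication data already collected. The downside is a stated departure from treatment policy for this event and possibly a slightly lower response rate. If the redacted text already contains such a rule, only the reconciliation, the therapy-use summary and the SAP 15 entry remain.
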